5.4.2 Clinical Laboratory Data

The following clinical laboratory parameters are assessed in the protocol:

- Hematology (CBC): hemoglobin, hematocrit, platelet count, red blood cell count, WBC count (with differential).
- Blood chemistry: sodium, potassium, chloride, alkaline phosphatase, lactate dehydrogenase, gamma glutamyl transferase, blood urea nitrogen, creatinine, bicarbonate.
- Liver function tests: serum transaminases (ALT and AST), and bilirubin levels.

Hematology. Clinically significant abnormalities for selected hematology parameters will be tabulated and listed; the number and percent of subjects for these abnormalities will be provided. The criteria of the potentially significant hematology laboratory abnormalities are provided below.

Table 1 Criteria for Potentially Clinically Significant Hematology Abnormalities

Test	Criteria
White blood cell count (10 ⁹ cells/L)	<3.0; >=16.0
Lymphocytes (10 ⁹ cells/L)	<0.8; <0.5; >12.0
Segmented neutrophils (10 ⁹ cells/L)	<=1.0; <1.5; >=12.0
Red blood cell count (10 ¹² cells/L)	<=3.3; >=6.8
Hemoglobin (g/L)	<=100
Platelets (10 ⁹ cells/L)	<=100; >=600

Furthermore, selected hematology parameters will be listed and flagged by CTCAE grade, using the following categorization, if there is sufficient data.

Table 2 Severity Grades for Hematology

Test	Grade 1	Grade 2	Grade 3	Grade 4
Hemoglobin (g/L)	[100, LLN)	[80, 100)	[65, 80)	<65
Lymphocytes (10 ⁹ cells/L)	[0.8, LLN)	[0.5, 0.8)	[0.2, 0.5)	<0.2
Platelets (10 ⁹ cells/L)	[75, LLN)	[50, 75)	[25, 50)	<25
Segmented neutrophils (10 ⁹ cells/L)	[1.5, LLN)	[1.0, 1.5)	[0.5, 1.0)	<0.5
White blood cell count (10 ⁹ cells/L)	[3.0, LLN)	[2.0, 3.0)	[1.0, 2.0)	<1.0

Liver function tests (LFT). Listings will be generated for alkaline phosphatase, ALT, AST, GGT and total bilirubin for each subjects by visit, where severity of abnormal values will be flagged based on the following table. Additionally, the incidence of ALT and/or AST elevations >=3X ULN by concurrently elevated total bilirubin will also be summarized.

Table 3 Severity Grades for Liver Function Tests

Test	Grade 1	Grade 2	Grade 3		Grade 4
ALT	(1.0, 3.0)	[3.0, 5.0]	(5.0, 10.0]	(10.0, 20.0]	>20.0
AST	(1.0, 3.0)	[3.0, 5.0]	(5.0, 10.0]	(10.0, 20.0]	>20.0
Alkaline phosphatase	(1.0, 2.5]	(2.5, 5.0]	(5.0, 20.0]		>20.0
GGT	(1.0, 2.5]	(2.5, 5.0]	(5.0, 20.0]		>20.0
Total bilirubin	(1.0, 1.5]	(1.5, 3.0]	(3.0, 10.0]		>10.0

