## 4.2. Schedule of Assessments

The schedule of assessments is presented in [Table 1](#). Assessment time points include an enrollment visit, a baseline visit, and follow-up visits at Months 1, 3, 4, 6, 9 and 12. An additional safety assessment will be performed remotely 4 months after the last study treatment dose. Subjects who discontinue treatment early will still be evaluated during the safety follow-up visit (i.e., 4 months after treatment and study discontinuation). Subjects having tentative disability progression identified near the end of the core study (e.g., Month 12) will attend additional follow-up visits 12 and 24 weeks later to confirm progression.

Magnetic resonance imaging (MRI) scans will be performed at the enrollment visit (no later than 7 days prior to the first dose of daclizumab), and at Months 1, 4, 6 and 12. MRI scans will be performed under the supervision of a trained radiologist. Ad-hoc MRI scans may be performed as needed, such as in the event of a MS relapse, in order to rule out a progressive multifocal leukoencephalopathy (PML) diagnosis.

Blood chemistry and hematology assessments will be performed at baseline and at Months 1, 3, 6, 9 and 12. Hematology assessments will include a complete blood count (CBC). Liver function tests (LFT) [alanine transaminase (ALT)/ aspartate transaminase (AST)] will be done at enrollment and monthly visits. Bilirubin testing must be done together with the first AST/ALT test at the enrollment visit. Bilirubin testing must also be done if ALT/SGPT (serum glutamic pyruvate transaminase), or AST/SGOT (serum glutamic oxaloacetic transaminase)  $>3*$ upper limit of normal (ULN), since treatment must be permanently discontinued with the concomitant elevation of total bilirubin  $>2*ULN$ .

At the end of the study, liver monitoring will be done per routine clinical practice.

A safety follow-up visit at 4 months after the last dose of daclizumab provided by the study will be conducted remotely to evaluate potential delayed safety outcomes. The assessments during the additional safety follow-up period will include all safety endpoints described in [Table 1](#). Liver function tests (LFT) will be performed only if the subject is continuing daclizumab or if the subject is within 4 months since study treatment discontinuation, and monitoring is deemed appropriate by the Investigator.

CONFIDENTIAL

The information contained herein may not be used, disclosed, or published without the written consent of  

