## Efficacy and Safety of Daclizumab in Subjects with RRMS Switching from Natalizumab

1. Written informed consent must be obtained prior to start of the study.
2. Screening MRI should occur no later than 7 days prior to the first dose of daclizumab. For subsequent visits, MRI scan can be performed up to 4 days prior to the visit. Ad-hoc MRIs may be conducted as needed, such as in the event of a relapse to rule out PML diagnosis.
3. This is required only for females of child-bearing potential. A urine pregnancy test will be performed monthly.
4. Liver function tests (LFTs) are required to be performed monthly (either on-site or via home visits at Month 7, 8, 10 and 11, if applicable), and samples will be analyzed centrally for the purposes of this study. Results from either local or central LFT tests can be used for medical management of the patient and to determine whether dosing should continue or be suspended at the monthly dosing timepoint. In cases where local LFTs were performed, samples must also be collected for central analysis.
5. Liver function tests (LFTs) during the safety follow-up will be performed only if the subject is continuing daclizumab or if the subject is within 4 months since study treatment discontinuation, and monitoring is deemed appropriate by the Investigator; Abnormal AST/ALT values as described in the product label will lead to treatment suspension or discontinuation.
6. [REDACTED]
7. Samples will be analyzed centrally.
8. Daclizumab dosing will start at baseline and occur monthly until Month 11. Doses at baseline and Months 1, 2, 3, 4, 5, 6 and 9 will be administered in the clinic, and doses at Months 7, 8, 10 and 11 can be administered at home or in the clinic. Daclizumab dosing will not begin until a minimum of 28 days have passed since last natalizumab dose. Before a monthly dose of daclizumab is given, LFT results from a prior test performed within the previous 28 (+3) days must be reviewed by the Study Neurologist or their backup.
9. Subjects will be provided a dosing diary at the Month 6 and Month 9 visits to record observations for home dosing only; home dosing is possible for Month 7, 8, 10, and 11. A window of  $\pm 4$  days applies to daclizumab dose even if it is done at home; subjects should be appropriately instructed on daclizumab self-administration using the autoinjector.

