#### 6.1.2. Secondary Objectives and Endpoints

The secondary objectives of this study in this study population are to evaluate the effects of daclizumab on the following:

- MS relapse activity including the ARR and the proportion of subjects experiencing relapses requiring hospitalization and/or steroid treatment.
- MS-related outcomes measured using MRI.
- Safety and tolerability in subjects previously treated with natalizumab.

The secondary endpoints that relate to these objectives are the following:

- The proportion of subjects relapse-free at Month 12.
- The proportion of subjects experiencing relapse requiring hospitalization and/or steroid treatment at Month 12.
- The ARR at Month 12.
- The number of new Gd+ enhanced and T1 hypointense lesions at Month 6 and Month 12 on MRI.
- The number of new or newly enlarged T2 hyperintense lesions at Month 6 and Month 12 on MRI.
- The permanent discontinuation rate of daclizumab at Month 12.
- The incidence of AEs and SAEs including clinically relevant shifts in clinical laboratory assessments.

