#### **13.5.2.4. Laboratory Data**

Laboratory data will be summarized using shift tables. Shifts from baseline to high/low status for hematology and blood chemistry parameters will be presented. In addition, the shift from baseline to the maximum post-baseline value and the shift from baseline to the minimum post-baseline status will be presented for each laboratory test by treatment group. Summary statistics for actual values and change from baseline will also be presented for quantitative laboratory data.

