4.1 Treatment Period Definitions

Based on the schedule of assessment, we have the following definitions:

- **the first dosing date** is the date when the subject is first dosed;
- **the last dosing date** is the date of the last date the subject is dosed;
- **The end of study date** is the last visit date;

- **Treatment period, or, time on (study) treatment**, is defined as the time between the first dosing date and the last dosing date; it is calculated as the last dosing date minus the first dosing date + 1; also known as the time exposed to study drug;
- **Time on study, or study period**, is defined as the time between the first dosing date and the end of study date, calculated as the last visit date – the first dosing date + 1.

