4.3 Demographics and Baseline Characteristics

Demographic data, including age (years), age category (<18, 18-19, 20-29, 30-39, 40-49, 50-55, and >55, also ≤ 35 , > 35), gender, race category, baseline height (cm) and weight (kg) will be summarized.

Baseline data are defined as data collected on the closest date prior to or on the first dosing date. Baseline disease characteristics will be summarized. These include years since disease (MS) onset, years since diagnosis, McDonald criteria, number of relapses in the past 12 months and in the past 3 years, [REDACTED], [REDACTED], baseline MRI, prior MS treatment history, medical history, tobacco use, and status of interferon binding and neutralizing antibodies. Additional variables may be included where applicable.

All demographic and baseline data will be summarized for the full analysis set.

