5.4 Safety Analysis

Safety analysis will be performed with data from the entire study period.

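### SAP 5.4.2 counts hematology abnormalities with no post-baseline or worsening condition, and omits the laboratory shift analysis without saying so

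*SAP*

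**What the plan says.** **The count.** SAP 5.4.2 states: "Clinically significant abnormalities for selected hematology parameters will be tabulated and listed; the number and percent of subjects for these abnormalities will be provided". SAP Table 1 supplies fixed cut-offs for six blood-count parameters. Table 2 adds severity grades, to be flagged in a listing if data suffice. Neither refers to baseline.

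**The window.** SAP 5.4 states: "Safety analysis will be performed with data from the entire study period". Under SAP 4.1 the study period "is defined as the time between the first dosing date and the end of study date", with the first dosing day itself counted.

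**The baseline sample.** SAP 4.3 states: "Baseline data are defined as data collected on the closest date prior to or on the first dosing date". Protocol 4.2 states: "Blood chemistry and hematology assessments will be performed at baseline and at Months 1, 3, 6, 9 and 12". Note 8 to Protocol Table 1 states: "Daclizumab dosing will start at baseline and occur monthly until Month 11". Table 1 schedules no blood count at the enrollment visit.

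**The shift analysis.** The last secondary endpoint in Protocol 6.1.2 reads: "The incidence of AEs and SAEs including clinically relevant shifts in clinical laboratory assessments". Protocol 13.5.2.4 plans the matching analysis: "Shifts from baseline to high/low status for hematology and blood chemistry parameters will be presented". It adds shifts to the highest and lowest post-baseline values, and change from baseline. SAP 5.4.2 contains none of these. The corresponding bullet in SAP 1.2 stops before its laboratory part is named.

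**The concern.** A table of subjects with abnormal hematology in a single-arm study will be read as what happened on daclizumab. If the window contains the baseline sample and no rule refers back to it, the table mixes abnormalities present at the start with those that arose later. The percentage cannot tell them apart.

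The planned shift table would have made the distinction, because it cross-classifies each subject's baseline status with later status. Its absence removes that safeguard and leaves the laboratory part of a secondary endpoint without its prescribed analysis.

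The plan uses a baseline reference elsewhere. SAP 5.4.1 limits adverse-event tables to events that start on treatment or worsen after it begins. Protocol 13.5.2.6 limits its vital-sign count to abnormalities after baseline.

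**Working it through.** The plan states no figure for this point, so there is none to reproduce. The check is a comparison of passages, followed by simple arithmetic on size.

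**Step 1. Is the baseline blood count inside the window?**
- The window opens on the first dosing date and includes it (SAP 5.4 with 4.1).
- The first dose is given at the baseline visit, Day 0 (Protocol Table 1, note 8).
- The first scheduled blood count is also at Day 0 (Protocol 4.2 and Table 1).
- A record on the first dosing date qualifies as baseline (SAP 4.3).

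The Day 0 blood count is therefore the baseline value and also falls within the period used for safety analyses. SAP 5.4.2 does not exclude it. This is inferred from four provisions read together; no single sentence states it.

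**Step 2. Is the shift analysis dropped openly?** SAP 4 says in general terms that termination means some endpoints will not be analyzed and some will only be listed. It does not mention laboratory shifts. The only secondary endpoint expressly declared not analyzed is the discontinuation rate (SAP 5.2).

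**Step 3. What remains for chemistry?** SAP 5.4.2 lists alkaline phosphatase, ALT, AST, GGT and total bilirubin by visit with grades. Seven other analytes are named as assessed and get no specific analysis there: sodium, potassium, chloride, lactate dehydrogenase, blood urea nitrogen, creatinine and bicarbonate. The general summary statistics of SAP 4.6 cover them where applicable.

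**Step 4. How large could the effect be?** Take N = 30 (SAP 4, approximate). For any one Table 1 criterion, let q be the share meeting it at Day 0 and e the risk of newly meeting it among the rest. Neither is in the documents; both are assumed. Suppose everyone has a post-baseline sample and no one abnormal at baseline worsens.
- Count with Day 0 included and no baseline condition: q + (1 − q)e.
- Count of new abnormalities over all subjects: (1 − q)e.
- Difference: q. One subject is 1/30 = 3.3 points.

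| q | e | Day 0 included | New only |
|---|---|---|---|
| 0% | 5% | 5.0% | 5.0% |
| 5% | 5% | 0.05 + 0.95 × 0.05 = 9.8% | 4.8% |
| 10% | 5% | 0.10 + 0.90 × 0.05 = 14.5% | 4.5% |
| 20% | 5% | 0.20 + 0.80 × 0.05 = 24.0% | 4.0% |
| 10% | 10% | 0.10 + 0.90 × 0.10 = 19.0% | 9.0% |

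The chance that at least one of 30 independent subjects is abnormal at Day 0 is 1 − (1 − q)^30: 0.79 for q = 5% and 0.96 for q = 10%.

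**Step 5. Effect of short follow-up.** Leaving aside the early-discontinuation visit, Day 0 is 1 of 6 scheduled blood counts through Month 12 (17%), 1 of 4 through Month 6 (25%) and 1 of 3 through Month 3 (33%). Early termination raises its weight.

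**The case against.** The strongest defence is that the study was stopped when the drug was withdrawn, about 30 subjects had enrolled, and the SAP announces a shortened report. Trimming is visible elsewhere: the vital-sign abnormality table in Protocol 13.5.2.6 becomes a by-subject listing in SAP 5.4.3. The hematology abnormalities are to be listed as well as tabulated, so a careful reader may be able to see which were present at Day 0. SAP 4.3 also classes Day 0 records as baseline, and a programmer might exclude them from the count unprompted.

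Much of this stands as mitigation. It does not explain why the table was kept without a baseline condition, and it does not amount to a declaration that the shift analysis is dropped.

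Several stronger readings are tempting, but the documents do not support them:
- **Chemistry outside the liver panel goes unreported.** SAP 4.6 promises summary statistics for safety parameters where applicable. What is missing is a specific analysis or listing.
- **Lymphocytosis after natalizumab will inflate the table.** Protocol 8.2 (exclusion 9) does name it as a known association. But the SAP Table 1 lymphocyte cut-offs are >12.0, <0.8 and <0.5. Nothing shows values above 12.0, and raised counts make the low cut-offs less likely to be met.
- **The secondary endpoint is not answered.** Its main part, the incidence of adverse and serious adverse events, is planned in SAP 5.4.1. Only the laboratory-shift part lacks its prescribed analysis.
- **Pre-dose abnormalities are certain to be counted and attributed to daclizumab.** The counting is inferred, the blood count is not stated to be drawn before the dose, and the SAP makes no attribution.

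**Conclusion.** The concern holds in two parts. First, as written, SAP 5.4.2 permits a baseline abnormality to be counted as an on-study one. The excess for any criterion equals the share of subjects meeting it at Day 0, at 3.3 points per subject if N is 30. That share is not in the documents, so the percentages under working are illustrations only. Second, the shift analysis in Protocol 13.5.2.4 is omitted without a statement that it is dropped.

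The clipped bullet in SAP 1.2 may be a typing slip or a loss in reading the PDF. The second part does not depend on it, because the protocol text is complete and SAP 5.4.2 has no shift analysis.

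The impact is modest and confined to laboratory safety reporting. A baseline reference would separate pre-existing from new abnormalities. In a single-arm study it cannot fully separate a daclizumab effect from natalizumab wash-out, and should not be presented as doing so. The change is still worth making, because it uses data already collected and makes the reported percentage interpretable.

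**What to change.** 1. In SAP 5.4.2, count only values after the first dose that newly meet a Table 1 criterion, or worsen by at least one Table 2 grade, relative to the last baseline value. Use subjects with at least one post-baseline value as the denominator. Table 2 grades only low values of five tests, so red cell count and the high cut-offs rely on new crossing alone.
2. Restore a hematology table of baseline status against worst post-baseline status, or a shift listing given about 30 subjects.
3. Add a by-subject listing with baseline status for the seven chemistry analytes outside the liver listing.
4. Complete the last endpoint sentence in SAP 1.2 to match Protocol 6.1.2.

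If the sponsor means to drop the shift analysis because of termination, SAP 5.4.2 should at least say so, as SAP 5.2 does for the discontinuation rate.

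The cost is SAP wording, a listing and one extra table shell in a shortened report. No new data are needed.

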5.4.3 Vital signs

Vital sign data will be listed for each subject by visit.
